11.2.2 SERIOUS ADVERSE EVENTS

Serious Adverse Event (SAE): An SAE, as defined by the NIH, consists of adverse events that result in death, require either inpatient hospitalization or the prolongation of hospitalization, are life-threatening, result in a persistent or significant disability/incapacity or result in congenital anomaly/birth defect. Other important medical events, based upon appropriate medical judgment, may also be considered Serious Adverse Events if a trial participant's health is at risk and intervention is required to prevent an outcome mentioned.

All SAEs will be recorded on the Serious Adverse Events Form (Appendix B), documented in the UE/SAE log and reported to the IRB. The SAE Form will be completed by the study coordinator, and includes information relating to the onset and nature of the SAE, relationship to the study treatment, seriousness of the SAE, treatment required as a response to the SAE, and outcome. This form will be filed in the participant's folder at the resolution of the event. The study coordinator will complete the UE/SAE log (Appendix D) which includes information such as the date of the event, time at which the study team was informed of the event, details, when the IRB was notified, and the date that the SAE form was completed.

11.2.3 UNANTICIPATED PROBLEMS

Unexpected Events (UE) will be recorded on the UE/SAE log (Appendix D) and will include information such as the date of the event, when the study team was informed of this event, details of the event, when the IRB was notified, and whether the SAE form was completed. The IRB will be notified of each UE that may occur during the study.

The Office for Human Research Protections (OHRP) considers unanticipated problems involving risks to subjects or others to include, in general, any incident, experience, or outcome that meets all of the following criteria:

- unexpected (in terms of nature, severity, or frequency) given (a) the research procedures that are described in the protocol-related documents, such as the IRB-approved research protocol and informed consent document; and (b) the characteristics of the subject population being studied;
- related or possibly related to participation in the research (in the guidance document, possibly related means there is a reasonable possibility that the incident, experience, or outcome may have been caused by the procedures involved in the research); and
- suggests that the research places subjects or others at a greater risk of harm (including physical, psychological, economic, or social harm) than was previously known or recognized.

If an UE occurs the IRB will be notified and the study will be adjusted as needed to protect the health and safety of the participants. Depending on the nature of the UE, the research protocol, inclusion/exclusion criteria, and informed consent will be changed to reflect the possibility of this event reoccurring. During this time, no new participants will be recruited and the research procedures for currently enrolled participants will be stopped. Each UE will be recorded and reported throughout the study.

11.3 REPORTING PROCEDURES

We will be adopting the OHRE’s “Reporting New Safety Information” SOP (SOP #1401):

What Event is Reported	When is Event Reported	By Whom the Event is Reported	To Whom the Event is Reported
Fatal or life-threatening unexpected, suspected serious adverse reactions	Within 7 calendar days of initial receipt of information	Investigator	UNC IRB
Non-fatal, non-life threatening unexpected, suspected serious adverse reactions	Within 7 calendar days of initial receipt of information	Investigator	UNC IRB/Institutional Officials, DSMB
Unanticipated adverse device effects	Within 7 calendar days of investigator first learning of effect	Investigator	UNC IRB
Unanticipated problem that is not an SAE	Continuing Review	Investigator	UNC IRB/Institutional officials
All protocol deviations that did not harm subject(s) or others or place subject(s) or others at increased risk of harm	Continuing Review	Investigator	UNC IRB

11.3.1 REPORTING OF PREGNANCY

Pregnancy tests will be administered on Visit 1 of Stimulation to all women of child-bearing potential (CBP). Within the study target population (ages 18-35), menstruating females, regardless of age are considered “CBP”. Women who have had a hysterectomy or a bilateral oophorectomy are not considered of “CBP”. There are no studies that suggest CF-tACS would interfere with pregnancy. However, should a participant become pregnant during the study, her participation will be immediately terminated.

11.4 TYPES AND DURATION OF FOLLOW-UP OF PARTICIPANTS AFTER ADVERSE EVENTS

The study coordinator will follow up within one week of an adverse event by a phone call.

12 STATISTICAL PLAN

The statistician for this study is [name].

12.1 STUDY HYPOTHESIS

NULL HYPOTHESIS. The change in task-performance for the cognitive control task is not significantly modulated by CF-tACS relative to sham tACS.

ALTERNATIVE HYPOTHESIS. CF-tACS induces an enhancement in task-performance during the cognitive control task by increase phase-amplitude coupling. This enhancement in performance is frequency specific. Theta-gamma CF-tACS modulates performance as a function set-size. Delta-beta CF-tACS modulates performance as a function of abstraction.

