4 BASIC STUDY DESIGN

The design for this study is a pilot, randomized, double-blind, sham-controlled, crossover clinical trial which will be used to demonstrate feasibility and collect effectiveness data for further refinement of CF-tACS approach and for the subsequent design of a follow-up, multi-site, large scale study. We are seeking 24 healthy participants, both male and female, between the ages of 18-35. All women of child-bearing potential (defined as menstruating women of all ages) will be asked to take a pregnancy test during the initial session in order to determine eligibility for the study. We estimate 2 months to complete study enrollment.

The experimental design is a 3-treatment, 3-period, 3-sequence crossover with a 1 week washout interval between periods. N=24 participants will be enrolled and allocated by stratified randomization to six treatment sequences, S-At-Ad, S-Ad-At, At-S-Ad, At-Ad-S, Ad-S-At, Ad-At-S. S refers to Sham Regimen which is 40 minutes of sham CF-tACS, At refers to Active Theta-Gamma Frequency Regimen which is 40 minutes of verum CF-tACS, and Ad refers to Active Delta-Beta Frequency Regimen which is 40 minutes of verum CF-tACS.

Participants will be randomly assigned to one of 6 sequences on the first visit.

Sham treatment will include 10 seconds of ramp-in to 1 minute of CF-tACS with a ramp-out of 10 seconds for a total of 80 seconds of stimulation. The 80 seconds of stimulation serves to desensitize the scalp beyond which participants are generally not able to tell apart the presence or absence of stimulation. This strategy has been described in previous studies using tACS (Alekseichuk et al. 2017; Mellin et al. 2018). Verum CF-tACS will have a 10 second ramp-in and ramp-out with 5 minutes of stimulation, for 8 separate blocks with a minimum 3 minute break between each block, for a total of 2560 seconds of stimulation. Stimulation waveform is coupled frequency with a low frequency component and brief high frequency component on each cycle with maximum amplitude of 2 mA.

Eligible participants will have a total of 4 visits, each lasting approximately 3 hours and separated by at least 1 week. Total participation will include about 12 hours over the course of four weeks. All time estimates take into consideration breaks and time variance in administration.

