7 STUDY OUTCOMES

7.1 PRIMARY OUTCOMES

The cognitive task will consist of 400 trials. The EEG recorded simultaneously with the task will be analyzed following an established preprocessing pipeline to remove artifacts related to eye movements, eye blinks, heart beats and muscle activity. The oscillation power and phase will be estimated using Morlet wavelet convolution. The primary outcome is phase-amplitude coupling between the stimulated frequencies (measured from EEG), reaction time, and accuracy. Phase amplitude coupling will be calculated using the phase locking value z-corrected based on a boot-strapped null distribution from randomly shifting the amplitude values 1000 times (see Cohen *Analyzing Neural Time Series Data* 2014 for method).

Our primary outcomes:

- Theta-gamma tACS will increase theta-gamma phase amplitude coupling (one-tailed, Student's t-test)
- Delta-beta tACS will increase delta-beta phase amplitude coupling (one-tailed, Student's t-test).
- Theta-gamma tACS will alter behavior (reaction time or accuracy) as a function of set-size (Student's t-test).
- Delta-beta tACS will alter behavior (reaction time or accuracy) as a function of abstraction (Student's t-test).

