12.2 STATISTICAL ANALYSIS PLANS

Statistical analyses will be performed to test the null hypothesis indicated in section 2.4 *Study Aims/Hypothesis*.

The cognitive task will consist of 400 trials. The EEG recorded simultaneously with the task will be analyzed following an established preprocessing pipeline to remove artifacts related to eye movements, eye blinks, heart beats and muscle activity. The oscillation power and phase will be estimated using Morlet wavelet convolution. The primary outcome is phase-amplitude coupling between the stimulated frequencies (measured from EEG), reaction time, and accuracy. Phase amplitude coupling will be calculated as the phase locking value corrected for spurious noise using a boot-strapped null distribution (see Cohen Analyzing Neural Time Series Data 2014 for method).

Our primary outcomes and their test are described below:

- Theta-gamma tACS will increase theta-gamma phase amplitude coupling (one-tailed, Student's t-test)
- Delta-beta tACS will increase delta-beta phase amplitude coupling (one-tailed, Student's t-test).
- Theta-gamma tACS will alter behavior (reaction time or accuracy) as a function of set-size relative to sham-tACS (Student's t-test).
- Delta-beta tACS will alter behavior (reaction time or accuracy) as a function of abstraction relative to sham-tACS (Student's t-test).

As exploratory analysis, linear mixed-effects models with BDNF genotype, sex hormone levels, as factors in addition to the variables condition and period will be fit with the rest of the analysis following what is described for primary analysis.

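### Section 12.1 hypothesises a frequency-specific performance effect, but no planned test compares the two active regimens on either task dimension

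*Combined protocol and SAP*

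**What the plan says.** Section 12.1 frames the null against sham: the change in performance "is not significantly modulated by CF-tACS relative to sham tACS". The alternative goes further. It says "This enhancement in performance is frequency specific" and then "Theta-gamma CF-tACS modulates performance as a function set-size. Delta-beta CF-tACS modulates performance as a function of abstraction".

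The planned analyses that touch on this are:

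- Section 7.1 lists "Theta-gamma tACS will alter behavior (reaction time or accuracy) as a function of set-size" and pairs delta-beta with abstraction in the same way. It names no comparator.
- Section 12.2 adds the comparator: "Theta-gamma tACS will alter behavior (reaction time or accuracy) as a function of set-size relative to sham-tACS" and "Delta-beta tACS will alter behavior (reaction time or accuracy) as a function of abstraction relative to sham-tACS", each by Student's t-test.
- The secondary outcomes (7.2) are correlations between coupling and behaviour. The exploratory outcomes (7.3) concern spectral power and coherence.
- As an exploratory analysis in 12.2, "linear mixed-effects models with BDNF genotype, sex hormone levels, as factors in addition to the variables condition and period will be fit". This model has a condition factor, but it names no task dimension and no contrast between the active regimens.

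Under section 4, participants are "allocated by stratified randomization to six treatment sequences, S-At-Ad, S-Ad-At, At-S-Ad, At-Ad-S, Ad-S-At, Ad-At-S", so each is due to receive sham and both active regimens.

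No section names a theta-gamma versus delta-beta comparison of performance, a test of either regimen on the other's dimension, or a regimen-by-dimension interaction.

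**The concern.** Frequency specificity is a statement about how the two active regimens differ. A regimen that beats sham on its own dimension shows that stimulation did something there. It does not show that the other regimen would have done less. One regimen being significant and the other not would not show it either.

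The rival explanation that matters is narrow: a shared effect of stimulation that grows with task demand on both dimensions. Section 6.5.1 contrasts simple with complex control conditions, so dependence on demand is a relevant alternative. An effect equal at all levels of set-size or abstraction cancels in these tests and is not a threat.

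Two things are at stake. The 12.1 statement might be read as supported by two sham comparisons that do not bear on it. And section 2.4 wants the pilot to supply estimates for a larger study, yet the active-versus-active difference in performance, which a trial of specificity would be planned on, is not a named estimate.

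**Working it through.** **Inputs.** From section 12.3: n = 24, alpha 0.05, effect sizes d = 0.48 and 0.6. The following are assumptions, because the documents give no SDs or correlations:

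- d is a standardised paired difference, applied here to a change in a set-size or abstraction effect. Section 12.3 conjectures it from an earlier study of task accuracy and resting-state connectivity.
- Every paired difference between two conditions has SD 1, active versus active included.
- The two dimensions are independent or have correlation 0.5, and all 24 participants contribute.
- Behavioural tests are two-sided, because 12.2 marks only the coupling tests as one-tailed.

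**1. The plan's own power figures.** For a paired t-test the noncentrality is d × √24, with 23 degrees of freedom: 0.48 × 4.899 = 2.35 and 0.6 × 4.899 = 2.94.

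- Two-sided power: 61.5% and 80.4%.
- One-sided power: 73.8% and 88.6%.

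Section 12.3 states more than 60% and more than 85%. Two-sided, the first holds and the second does not. One-sided, both hold as lower bounds. The present point does not depend on this.

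**2. What each contrast estimates.** Take each participant's set-size effect and abstraction effect (performance at the high level minus the low level) under each condition. TG is theta-gamma and DB is delta-beta. The entries are mean differences in those effects.

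| Scenario | TG − sham, set-size (planned) | DB − sham, abstraction (planned) | TG − DB, set-size (not planned) | DB − TG, abstraction (not planned) |
|---|---|---|---|---|
| Same shift at all levels | 0 | 0 | 0 | 0 |
| Full specificity | d | d | d | d |
| Half the effect off target | d | d | d/2 | d/2 |
| Shared, grows with demand on both | d | d | 0 | 0 |
| Both act on abstraction, only TG on set-size | d | d | d | 0 |

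The last four rows are identical in the planned columns. Only the unplanned columns separate them.

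**3. How often both sham tests are positive (independent dimensions).**

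- Full specificity: 0.615² = 0.378 and 0.804² = 0.646.
- Equal shared demand-dependent effect: the same, 38% and 65%. At correlation 0.5 both scenarios give about 41% and 66%.
- Shared effect of half that size (d = 0.24, 0.30): power per test is about 20% and 29%, so both are positive in about 4% and 8%.
- Uniform effect: 0.05² = 0.25%.

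**4. Power of the missing contrasts.**

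- One direct contrast, no off-target effect: mean d, so about 61% and 80%.
- One direct contrast, half the effect off target: d − d/2 = d/2, so about 20% and 29%.
- Both sham tests and both direct contrasts significant under full specificity (simulated crossovers with a shared sham session): about 17–20% at d = 0.48 and 45–48% at d = 0.6, across correlations 0.5 and 0.

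**5. Why an interaction should not decide the claim.** In the last row of the table the regimen-by-dimension interaction has mean (d − 0) − (d − d) = d, although the abstraction effect is not specific at all. Consider a rule that asks for both sham tests, a significant interaction, and direct contrasts that merely have the right sign. By simulation it would conclude two-way specificity in about 16% (d = 0.48) or 30% (d = 0.6) of such trials, and 19% or 33% at correlation 0.5. Requiring both direct contrasts to be significant brings this to 1–2% or less.

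**The case against.** - **The planned tests match the null.** The null in 12.1 is against sham, and 12.2 sets no rule that declares specificity from two positive sham tests. This stands. A reader might infer that the plan will draw a false conclusion about specificity. The documents do not support that: they leave the hypothesis untested rather than wrongly tested.
- **The shared effect is hypothetical.** This also stands. A reader might infer that such an effect is likely, or that any non-specific effect would mimic specificity. No passage suggests or sizes one, and a uniform effect cancels. The equal 38% and 65% follow by construction, since the planned tests never use off-target data. They show the logic, not the probability of harm.
- **It is a pilot meant to generate hypotheses.** This argues for estimates with intervals over elaborate decision rules, and the fix follows it. It does not excuse leaving out the estimate on which the stated hypothesis turns.
- **The mixed model includes condition.** It is exploratory, built around genotype and hormones, and names neither task dimension nor an active-versus-active contrast. It does not fill the gap.
- **Section 12.1 never says that a regimen leaves the other dimension untouched.** Correct. The direct contrast asks whether a regimen acts more strongly than the other on its own dimension. It does not show a zero off-target effect, and 12.1 does not require one.
- **The same could be said of coupling.** A reader might extend the criticism to phase-amplitude coupling, but the specificity sentence in 12.1 is about performance. The plan makes no such claim for coupling.

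**Conclusion.** The point holds as a mismatch between a stated hypothesis and the planned analysis. Section 12.1 claims frequency-specific performance effects. The behavioural tests in 7.1 and 12.2 cannot distinguish specificity from an equal shared effect that scales with demand on both dimensions, although the crossover provides the data to do so. That the gap exists depends on no numerical assumption.

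Its size can only be illustrated. Both sham tests are positive in about 38% or 65% of trials under either explanation at d = 0.48 or 0.6, falling to 4% or 8% if the shared effect is half as large. These figures rest on a borrowed effect size, equal SDs and an assumed correlation. The consequence is moderate: the change should be made, but nothing here undermines the comparisons with sham.

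**What to change.** In 12.2, mirrored in 7.1:

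1. Name two within-participant contrasts: the theta-gamma minus delta-beta difference in the set-size effect, and the same difference in the abstraction effect. Use one behavioural measure, chosen in advance, and fix the predicted sign of each, because 12.2 says only that behaviour will alter. Report each with a 95% confidence interval. Each contrast stays within one dimension, so no common scale is needed.
2. State that a dimension shows a frequency-specific effect only if the regimen's test against sham and the direct contrast on that dimension are both significant in the predicted direction. The two-way mapping is supported only if this holds on both dimensions. Otherwise report effects versus sham and call specificity unresolved.
3. A regimen-by-dimension interaction may be reported as support, but should not decide the claim alongside direct contrasts judged on sign alone.

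Alternatively, limit 12.1 to effects relative to sham and report the two differences as pilot estimates.

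Either route costs wording and two contrasts from data already planned, with no added visits or participants. It should be settled before unblinding. The price of the first route is a stricter claim at low power: even under full specificity the two-way mapping would be supported in only about 17–20% (d = 0.48) or 45–48% (d = 0.6) of trials. The plan should therefore say that an unresolved result is not evidence that specificity is absent.

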12.2 STATISTICAL ANALYSIS PLANS

Statistical analyses will be performed to test the null hypothesis indicated in section 2.4 *Study Aims/Hypothesis*.

The cognitive task will consist of 400 trials. The EEG recorded simultaneously with the task will be analyzed following an established preprocessing pipeline to remove artifacts related to eye movements, eye blinks, heart beats and muscle activity. The oscillation power and phase will be estimated using Morlet wavelet convolution. The primary outcome is phase-amplitude coupling between the stimulated frequencies (measured from EEG), reaction time, and accuracy. Phase amplitude coupling will be calculated as the phase locking value corrected for spurious noise using a boot-strapped null distribution (see Cohen Analyzing Neural Time Series Data 2014 for method).

Our primary outcomes and their test are described below:

- Theta-gamma tACS will increase theta-gamma phase amplitude coupling (one-tailed, Student's t-test)
- Delta-beta tACS will increase delta-beta phase amplitude coupling (one-tailed, Student's t-test).
- Theta-gamma tACS will alter behavior (reaction time or accuracy) as a function of set-size relative to sham-tACS (Student's t-test).
- Delta-beta tACS will alter behavior (reaction time or accuracy) as a function of abstraction relative to sham-tACS (Student's t-test).

As exploratory analysis, linear mixed-effects models with BDNF genotype, sex hormone levels, as factors in addition to the variables condition and period will be fit with the rest of the analysis following what is described for primary analysis.

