12.3 SAMPLE SIZE DETERMINATION

Based on the study by Alekseichuk et al 2017 which investigated the effect of CF-tACS on task accuracy and resting state EEG connectivity in 20 healthy participants per crossover arm, we conjecture that our effect size is at least 0.48. With this effect size, our sample size of 24 has power greater than 60% with alpha 0.05. We have improved upon the experimental design in Alekseichuk et al 2017 by personalizing our stimulation frequencies to target the frequencies of peak phase-amplitude coupling during the task. With this methodological improvement, we expect our effect size to increase to 0.6 (see Romei et al. 2016). With this effect size, our sample size has power greater than 85%.

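### Two behavioural tests bear on the single null in 12.1 with no multiplicity rule (false-positive rate about 8–10%, not 5%, if either can reject it), and the 85% power in 12.3 does not hold for them if two-sided

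*Combined protocol and SAP*

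**What the plan says.** Section 7.1 and section 12.2 carry the same list of four primary hypotheses. Section 12.2 introduces it with "Our primary outcomes and their test are described below". The four are:

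- theta-gamma stimulation raises theta-gamma coupling (one-tailed);
- delta-beta stimulation raises delta-beta coupling (one-tailed);
- theta-gamma stimulation changes behaviour with set size (no tail stated);
- delta-beta stimulation changes behaviour with abstraction (no tail stated).

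Each behavioural item offers reaction time and accuracy as alternatives. No order, alpha split, adjustment or rule for combining the four results appears in section 7 or section 12.

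Section 12.1 gives one null: "The change in task-performance for the cognitive control task is not significantly modulated by CF-tACS relative to sham tACS". Its alternative is directional and brings in the mechanism: "CF-tACS induces an enhancement in task-performance during the cognitive control task by increase phase-amplitude coupling". It then assigns set size to one regimen and abstraction to the other. Section 12.2 refers the reader to section 2.4 for the null, but 2.4 lists only three aims.

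Section 12.3 has the only alpha: "our sample size of 24 has power greater than 60% with alpha 0.05", following "we conjecture that our effect size is at least 0.48". It then says "we expect our effect size to increase to 0.6" and "With this effect size, our sample size has power greater than 85" per cent. It does not say which of the four tests this describes, or whether that test is one- or two-sided.

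**The concern.** The plan gives no way to go from four p-values to a conclusion about the one null it states. Two of the tests, one per regimen, address task performance against sham, and nothing says whether one significant result is enough to reject a null that covers both regimens. If it is, the error rate for that null is above 0.05.

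The power statement has a related gap. A reader will apply it to any of the four tests, but they differ in sidedness, and the higher figure is reached only by a one-sided test.

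The consequences are practical. Section 7.2 runs its brain–behaviour correlations only for behavioural results that reach significance, and section 4 says the data will feed the design of a larger multi-site study.

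**Working it through.** **Inputs.** n = 24 and alpha = 0.05 (12.3). Effect sizes are 0.48 and 0.6 (12.3), taken as the standardised mean of the within-person difference, since the type is not stated. The design is a crossover (section 4), so the t-tests are taken as paired with 23 degrees of freedom. Dropouts are replaced (4.1.2), so 24 is the analysed number. Coupling tests are one-sided as stated, with sham assumed as comparator because 12.2 names none for them. Behavioural tests are read as two-sided because 12.2 predicts a change without a direction. The documents give no correlation between tests, so 0 to 0.8 is assumed.

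**Step 1: reproduce the stated power.** Power comes from the noncentral t with noncentrality d × √24, which is 0.48 × 4.899 = 2.35 or 0.6 × 4.899 = 2.94. Critical values are 1.714 (one-sided) and 2.069 (two-sided).

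| Effect | One-sided | Two-sided | Stated in 12.3 |
|---|---|---|---|
| 0.48 | 73.8% | 61.5% | above 60% |
| 0.6 | 88.6% | 80.4% | above 85% |

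Both stated bounds hold one-sided. Two-sided, the 60% bound holds and the 85% bound does not. An unpaired comparison with 24 per arm reaches only 51% one-sided or 38% two-sided at 0.48, so the paired reading is the one that fits.

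**Step 2: error rate for the 12.1 null.** Two behavioural tests, either sufficient, each two-sided at 0.05 on one measure. If independent: 1 − 0.95² = 9.75%. Simulated with n = 24 at correlation 0, 0.25, 0.5 and 0.8: about 9.9%, 9.5%, 9.0% and 7.8%.

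**Step 3: any of the four tests.** If independent: 1 − 0.95⁴ = 18.5%. Simulated with two one-sided and two two-sided tests at the same correlations: about 18.7%, 17.8%, 15.8% and 12.5%, with repeat runs at 0.8 giving up to 12.8%.

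**Step 4: if reaction time and accuracy are both tried.** The 12.1 null then has four two-sided tests: 18.5% if independent, about 11.6% at correlation 0.8. The whole list becomes six tests: 1 − 0.95⁶ = 26.5% if independent, about 21.5% at 0.5 and 15% at 0.8.

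**Step 5: cost of Holm over the two behavioural tests.** A test is rejected if its p ≤ 0.025, or if its p ≤ 0.05 and the other's p ≤ 0.025. Two-sided power at 0.025 is 70.4% for effect 0.6 and 49.3% for 0.48. With independent tests and the same effect in both:

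- 0.6: 0.704 + (0.804 − 0.704) × 0.704 = 77.4%
- 0.48: 0.493 + (0.615 − 0.493) × 0.493 = 55.3%

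Simulated at correlation 0.8, these fall to about 75.5% and 54.5%. The simulated chance of any false rejection under no effect is 5.0% at correlation 0 and 4.1% at 0.8.

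**The case against.** The strongest reply is that this is a pilot. Section 2.4 sets out to generate hypotheses and obtain planning estimates, and no passage defines a positive trial. The four tests are distinct, prespecified and frequency-specific, and section 7.2 seems to read the behavioural results one at a time. Testing each separately reported claim at its own 0.05 is a defensible choice, and 12.3 never presents its alpha as a familywise rate.

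Much of this stands. It rules out two stronger readings that a reader might infer.

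- *The trial has a 13–19% false-positive rate.* That is the chance of at least one false positive somewhere in the list. The coupling tests do not test a null about task performance, so the rate for the null in 12.1 is the 8–10% of step 2. For the same reason, a four-way correction is not clearly required.
- *All four tests must succeed, so power is about 51–70%.* Those figures follow if effect 0.6 applies to every test and the correlation runs from 0 to 0.8 (about 20–48% at 0.48). But no passage requires all four to pass. The alternative in 12.1 describes what is expected and is not a success rule.

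The pilot argument does not remove the rest. The plan labels the tests primary, states a null, an alpha and a power, and makes later analyses depend on significance. It might also be said that the behavioural tests are one-sided, since 12.1 expects enhancement. Power at 0.6 would then be 88.6% and the 85% claim would hold, but 12.2 does not say so and marks only the coupling tests as one-tailed.

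**Conclusion.** The concern holds in a limited form and should be corrected, though it does not undermine the study. The plan does not say how two behavioural tests decide one null. If either may reject it unadjusted, the error rate is about 8–10%, or 1.6 to 2 times 0.05, and higher if both reaction time and accuracy are tried. Separately, the power above 85% does not apply to a two-sided behavioural test, which reaches 80.4% even before any adjustment.

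The error rates depend on an assumed correlation of 0 to 0.8 and on the either-one-suffices reading, which the documents neither state nor exclude. The power figures depend on paired tests, 24 analysed participants and the effect-size meaning given above.

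**What to change.** 1. In 12.1 and 12.2 (and 7.1 to match), name one behavioural measure per regimen and its sidedness, and apply Holm at 0.05 across the two behavioural tests of the 12.1 null. Treat the two coupling tests as separate mechanism outcomes, reported with estimates and confidence intervals and not counted as evidence against that null. Correct the reference to 2.4 so that it points to 12.1.
2. Alternatively, in keeping with the aims in 2.4, report all four as estimates with confidence intervals, call none confirmatory, and remove the single-null wording from 12.1.
3. In 12.3, give power per test and per sidedness: 88.6% one-sided and 80.4% two-sided at 0.6, and 73.8% and 61.5% at 0.48. Say that these are unadjusted, and add the adjusted figures if Holm is used.

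This takes a few sentences and no new participants or data. The measure must be chosen first, because Holm over two tests does not hold 0.05 if the better of reaction time and accuracy is picked afterwards. With two-sided tests, the price of Holm is per-test behavioural power of about 75–77% instead of 80.4% at effect 0.6, and about 54–55% instead of 61.5% at 0.48.
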